### **9.2 *Weight and Caloric Intake:***

The primary and secondary efficacy outcomes of change in weight and caloric intake will be compared within each disease group and among the treatment groups using a shared-baseline linear mixed model for correlated, longitudinal assessments of weight with fixed effects of time and the treatment x time interaction and age, gender, and baseline swallowing score and their interactions with time included as covariates and random participant specific intercepts and slopes. Pairwise comparisons between treatment groups will be analyzed using linear contrasts from the full model, with correction for multiple comparisons vs. standard of care using Dunnett's method. Significant benefit from the eHealth or RD intervention will be declared if less weight is lost and the two-tailed p-value for comparison to standard of care is less than 0.027 for each intervention separately.

### **9.3 *Sample size calculation:***

Using the component estimates from weight data collected in the clinical trial of Ceftriaxone in ALS [13] the effective standard deviation for rate of change in weight assuming weight assessments every 2 weeks, an annual 23% mortality rate, and 20% loss to follow-up is 0.98 kg/month. Given a sample size of approximately 150 ALS participants randomized 1:1:1 to the two interventions and standard care will provide at least 80% power to detect a true 0.75-kg/month difference between each intervention arm and the control arm over 24 wks at a two-tailed  $p < 0.027$  using Dunnett's method (testing superiority of each intervention over standard care). Based on a non-inferiority bound of 0.5 kg/month, the study will have at least 80% power to declare the e-Health intervention non-inferior to in-person consultation with an RD based on a one-tailed test at  $p < 0.05$  and assuming that the two interventions are in fact equivalent.

**Accrual Targets:** We intend to enroll 3-4 ALS subjects per week for the first 12 weeks, after which the rate will slow to 2-3 subjects/week, in order to accommodate return schedules and telephone visits. It should take approximately 12 months to enroll 150 participants at an average rate of 10 subjects per month. PD and HD subjects will be enrolled separately based upon funding and infrastructure availability.

**Treatment Discontinuation Rate Targets:** Subjects who discontinue treatment will be considered treatment failures in the tolerability analysis. However if there is an elevated discontinuation or study drop-out rate, it will reduce the power to detect a significant treatment difference for the primary outcome. The Steering Committee will analyze enrollment and discontinuation rates at pre-specified intervals and if it appears that fewer than 25 subjects per arm will complete the 6 month study, they may recommend increasing the enrollment times or stopping early for futility.

### **9.4 *Tertiary and Exploratory Outcomes:***

Although the study is not powered to look at the effects of the diet interventions on disease progression, we will examine trends in measures of disease progression. Preliminary analyses of survival and disease-specific outcome measures (ALSFRS-R, UDysRS, UHDRS) will use the ITT sample. We will ascertain the final outcome measures of all subjects at the end of the study and every subject will be included in the analysis whether or not they elected to stop treatment before the end of the study.

Change in the disease-related outcomes will be compared among the treatment groups using the same shared-baseline linear mixed model used to analyze weights. Additional baseline measures that might independently predict rate of progression will be considered for inclusion as additional covariates based on review of data prior to analysis for treatment differences.

Survival during and after the study intervention will be analyzed using a Cox proportional hazards model for treatment assignment, adjusted for age, gender, duration of disease, and baseline BMI. Hazard ratios and their 95% confidence intervals will be used to interpret the regression results.

The exploratory outcome measures of biomarkers of body composition, lipid metabolism, and appetite regulatory hormones will be explored in the ITT and per-protocol samples. Change over time in fat mass, fat-free mass, albumin, pre-albumin, lipid levels, leptin, ghrelin, PYY, will be compared among the treatment groups using a shared-baseline linear mixed model with gender, treatment and BMI included as covariates. We hypothesize that weight gain in the intervention arms will result in increased lipid levels. Pairwise comparisons between treatment groups will be analyzed using linear contrasts from the full model.

### **9.5 Stopping for Safety**

The Principal Investigator is responsible for oversight of the data safety and will work with the Medical Monitor and study statistician to monitor the study and evaluate safety on an ongoing basis. Unblinded safety data will be presented to the Medical Monitor every 3 months during the study. Decisions to stop the trial, enrollment of one or more disease groups, or randomization of one of the intervention arms early for safety will be made by the Medical Monitor, Principal Investigator and study Statistician. There will be a rule for stopping if either nutritional counseling intervention appears to increase mortality relative to standard of care, where mortality is defined as death or initiation of permanent assisted ventilation. Survival in each counseling intervention arm will be compared to the standard of care arm using the logrank test. We will use an alpha spending rule to test for increased mortality with a cumulative 1-sided p-value of 0.1 separately for each disease group. By Dunnett's test, that equates to cumulative 1-sided p-values of 0.0574 for each intervention arm according to the following table:

Analysis	% of total follow-up completed	Z statistic	Cumulative Alpha	P-value to stop
1 (Interim)	33.3%	3.09103	0.000997	0.000997
2 (Interim)	66.7%	2.06168	0.019950	0.019619
3 (Final)	100%	1.63136	0.057404	0.051408

Thus, if at the first interim analysis, the p-value for the logrank test comparing the survival distributions of one of the interventions versus standard care is less than 0.000997, then this intervention arm would be stopped. Each intervention arm may be stopped early independently, without affecting continued enrollment and follow-up of participants in the other arms of the trial. The overall probability of stopping at least one arm of the trial early for a given disease group when there is in truth no effect on mortality is 10%. The probability of stopping at least one arm of the trial early across all three disease groups when there is no effect on mortality in

any is 27%. The first interim analysis will occur after one third of total expected follow-up is completed. This may vary depending on accrual rate and total accrual targets for each disease group.

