### **9.1 *Safety and Tolerability***

All randomized subjects will be considered evaluable for tolerability and safety. Subjects lost to follow-up will be considered treatment failures at the time they drop out of the study. The data will be reviewed by the independent Medical Monitor, using the considerations here as guidelines. Their recommendation would then be reviewed by the Principal Investigator.

Safety data will be summarized by disease group and treatment group and reported to the independent Medical Monitor every 3 months during the study. Total numbers of adverse events will be compared within each disease group and among treatment groups using negative binomial regression and the proportion of participants experiencing each type of event by Fisher's exact test. Every 3 months the Medical Monitor will review cumulative study reports to determine if there has been an excess rate of serious adverse events in any of the arms. At two interim analyses, mortality rates will be compared, and one or both intervention arms may be terminated for one or more disease groups according to pre-determined stopping rules described below.

In the tolerability analyses, a subject will be regarded as a treatment success if he/she complies with at least 80% of the nutritional counseling sessions, or enters at least 80% of the required electronic data.

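### Section 9.5 labels 10% and 27% as null chances of stopping an arm early, but both count the final analysis; the table implies at most 4.0% per disease group and 12.0% across three for a mortality-boundary crossing at an interim

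*Protocol*

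**What the plan says.** Protocol section 9.5 sets up an "alpha spending rule to test for increased mortality with a cumulative 1-sided p-value of 0.1 separately for each disease group". It adds: "By Dunnett's test, that equates to cumulative 1-sided p-values of 0.0574 for each intervention arm". A table then lists two interim analyses, at 33.3% and 66.7% of follow-up, and a final analysis at 100%. Cumulative alpha per arm is 0.000997, 0.019950 and 0.057404.

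Two sentences below the table summarise the rule when there is no mortality effect. The first puts the overall chance of halting "at least one arm of the trial early for a given disease group when there is in truth no effect on mortality is 10" percent. The second begins "The probability of stopping at least one arm of the trial early across all three disease groups" and gives 27%.

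Two other statements show what an early stop means here. Section 9.5 says: "Each intervention arm may be stopped early independently, without affecting continued enrollment and follow-up of participants in the other arms of the trial". Section 9.1 says: "At two interim analyses, mortality rates will be compared, and one or both intervention arms may be terminated". The SAP does not repeat the stopping rule or either percentage.

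**The concern.** An early stop of an arm can happen only while the trial is still running. The 10% equals the whole one-sided alpha for a disease group, and the table reaches its full per-arm value of 0.057404 only in the final row. By the second interim it has spent 0.019950 / 0.057404 = 35% of that alpha; the other 65% belongs to the final analysis. So the two percentages seem to describe a different event from the one named.

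At stake is a stated operating characteristic: how often the mortality rule would close an arm early when the intervention does no harm. These two sentences are the only place where the documents give it. No boundary, sample size or analysis depends on them.

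**Working it through.** **Inputs.** From the section 9.5 table: Z = 3.09103, 2.06168, 1.63136; follow-up fractions t = 1/3, 2/3, 1; cumulative alpha per arm = 0.000997, 0.019950, 0.057404. From sections 9.5 and 3.1: two intervention arms, each compared with standard care by the logrank test, with 1:1:1 allocation. Equal allocation and a shared control give correlation 0.5 between the two comparisons.

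**Step 1: reproduce the table.**
- 1 − Φ(Z) = 0.000997, 0.019619, 0.051407. The printed p-values to stop are 0.000997, 0.019619, 0.051408.
- Cumulative crossing for one arm, from a normal vector with correlation √(t_i/t_j) between looks: 0.000997, 0.01995, 0.05741. This matches the printed column.
- One-sided Dunnett with two comparisons, correlation 0.5 and total 0.10: 0.0574 per arm, as printed.

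**Step 2: reproduce the 10% and 27%.** Take both arms jointly, with between-arm correlation 0.5. For three independent disease groups use 1 − (1 − p)³.

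| Crossing by | One group, at least one arm | Three independent groups |
|---|---|---|
| Interim 1 | 0.19% | 0.58% |
| Interim 2 | 3.65% | 10.6% |
| Final | 10.02% | 27.2% |

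The 27% is also 1 − 0.9³ = 0.271. Both printed percentages appear only in the row that counts the final analysis.

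**Step 3: bound the interim crossing from the printed alpha alone.** The chance that at least one event occurs cannot exceed the sum of the separate chances, whatever their correlation.
- One disease group, two arms: 2 × 0.019950 = 0.0399, or 4.0%.
- Three disease groups, six arms: 6 × 0.019950 = 0.1197, or 12.0%.

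These lie below the stated figures by factors of at least 10 / 4.0 = 2.5 and 27 / 12.0 = 2.25.

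**Step 4: sensitivity to the correlation.** Crossing by interim 2, one group / three groups: 3.95% / 11.4% at correlation 0; 3.83% / 11.0% at 0.3; 3.65% / 10.6% at 0.5; 3.37% / 9.8% at 0.7.

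**Step 5: how far the nominal figures can be trusted.** They treat the logrank statistic as normal.
- ALS: 50 per arm at the 23% annual mortality in section 9.3 gives 50 × (1 − 0.77^0.5) = 6.1 expected deaths per arm over six months. Simulations under no effect gave 3.2% to 3.7% by interim 2, close to nominal.
- PD and HD: the documents give no mortality rate. The planned total of 75 to 150, if split equally, is 12.5 to 25 per arm. Assuming 20 per arm and 5% annual mortality, expected deaths are 20 × (1 − 0.95^0.5) = 0.5 per arm. If all d deaths in a comparison fall in the intervention arm, the logrank Z is about (d − d/2)/√(d/4) = √d. Crossing 2.06168 then needs d = 5, since √4 = 2.00 and √5 = 2.24. Simulation gave about 0.03%.

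With those assumed inputs the three-group interim figure is close to the ALS figure alone, so 10.6% could be well too high. It would rise with higher PD or HD mortality.

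**The case against.** The best defence is that this is loose wording and nothing more. The alpha is introduced as cumulative, the first of the two sentences speaks of an overall probability, and the p-value-to-stop column is filled in for the final row as well. On that reading *stop* means crossing at any look. The interim share can also be read off the table, and no decision depends on either percentage. Most of this is fair, and it is why the point is minor. It does not make the sentences correct: the event they describe is still an early stop, section 9.1 places termination of arms at the two interims, and the 27% sentence is not qualified as overall.

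Two further objections stand and set limits. First, a reader might take 4.0% and 12.0% as caps on every kind of early stop. They are not. Section 9.1 has the Medical Monitor review serious adverse events every three months, and section 9.5 leaves stopping decisions to the Medical Monitor, Principal Investigator and statistician. Such discretionary stops are outside the table. Second, a reader might take 10.6% as the true three-group figure. It needs large-sample theory and full enrolment of all three groups, yet section 9.3 says: "PD and HD subjects will be enrolled separately based upon funding and infrastructure availability". Step 5 shows how low the PD and HD contributions could be.

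A reader might also infer that the Medical Monitor or IRB would be misled into discounting a real signal. No passage says that either relies on these sentences.

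**Conclusion.** The two sentences are wrong as written. The 10% and 27% are nominal probabilities of crossing the mortality boundary at any analysis, including the final. For a crossing at an interim, the printed alpha gives at most 4.0% per disease group and 12.0% across three, and about 3.7% per group at correlation 0.5. The two bounds take the table's cumulative alpha as given and need no assumption on correlation or independence. The 3.7% also assumes equal allocation, approximate normality and information proportional to follow-up.

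The documents do not support inferring that the stopping rule itself is faulty: the Z values, spending and Dunnett split all reproduce. The error overstates the false early-stop risk and hides none. Severity is minor.

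**What to change.** In section 9.5:
- Relabel 10% and 27% as the nominal chance, with no mortality effect, of crossing a mortality boundary at any analysis including the final.
- Add that the chance of crossing at an interim is nominally about 3.7%, and at most 4.0%, per disease group, and that discretionary stops are not included.
- If a three-group interim figure is kept, give it as a nominal upper bound of 12.0% (about 10.6% under large-sample theory with three independent, fully enrolled groups). Note that it could be much lower where PD and HD deaths are few or those groups do not enrol.

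The cost is rewording two sentences. Boundaries, alpha spending, Dunnett split and analyses stay as they are.

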## **10. DATA COLLECTION AND ADVERSE EVENT MONITORING**

### **10.1 Records to be Kept and Project Organization**

The MGH NCRI Data Management group and the Biostatistics Center at the MGH will conduct data management, biostatistics, regulatory compliance, adverse event reporting. For the purposes of the study, all clinical data will be captured using the NeuroBANK™ data repository platform.

### **10.2 PURPOSE OF NEUROBANK™**

NeuroBANK™ is a collaboration and data repository platform maintained by the Massachusetts General Hospital (MGH) Neurological Clinical Research Institute (NCRI). The system conforms to the 21 CFR Part 11 and other guidance documents on computerized systems in clinical trials. This platform facilitates:

1. Capture of clinical and research data from neurologic patients for individual projects in a structured and secure system;
2. Aggregating and sharing uniform, deidentified and/or anonymized datasets for secondary analyses.

### **10.3 ROLE OF DATA MANAGEMENT**

Data Management (DM) is responsible for the development, execution and supervision of plans, policies, programs, and practices that control, protect, deliver, and enhance the value of data and information assets.

All data will be managed in compliance with applicable Sponsor and regulatory requirements. Site personnel will collect, transcribe, correct, and transmit the data onto source documents, Case Report Forms (CRFs), and/or other forms used to report, track and record clinical research data. DM is responsible for developing, testing, and managing clinical data management activities.

#### **10.3.1 Data Entry and Checks**

Data capture will be entered in a timely manner into the NeuroBANK™ Electronic Data Capture (EDC) System. Data capture is the responsibility of the staff at the site under the supervision of the Principal Investigator. During the study, the Site investigator must maintain complete and accurate documentation for the study.

The NeuroBANK™ platform provides password protection. An edit checking and data clarification process will be put in place to ensure accuracy of the data. Logic and range checks as well as more sophisticated rules may be built into the eCRFs to provide immediate error checking of the data entered. The system has the capability to automatically create electronic

queries for forms that contain data that are out of range, out of window, missing or not calculated correctly. The sites will only have access to the queries concerning their subjects.

### **10.3.2 Data Lock Process**

The platform will have the ability to lock the project-specific visits to prevent any modification of data once the project is closed. Once this option is activated, every user will have Read-Only access to the data. The database then will be transferred to the Biostatistics Center by unloading the relational MS SQL Server database to a SAS format for statistical analysis.

### **10.3.3 DATA HANDLING AND RECORD KEEPING**

The Principal Investigator is responsible to ensure the accuracy, completeness, legibility, and timeliness of the data reported. Data reported in the eCRF derived from source documents should be consistent with the source documents and discrepancies should be explained.

### **10.3.4 Database Security**

The MS SQL Server database is located on a secure database server. This server is located in a restricted area of the Partners Healthcare server farm and physical access to it is limited to authorized personnel only. Both database and Web servers are located on the Partners Healthcare network behind the firewall. Access to the data at the clinical site will be restricted and monitored through the system's software with its required log-on, security procedures and audit trail. The data will not be altered, browsed, queried, or reported via external software applications that do not enter through the protective system software. There will be a cumulative record that indicates, for any point in time, the names of authorized personnel, their titles, and a description of their access privileges. The record will be in the study documentation accessible at the site. Controls will be in place to prevent, detect, and mitigate effects of computer viruses on study data and software. The application utilizes SSL (Secure Sockets Layer) technology and 128-bit encryption to comply with requirements of 21 CFR Part 11 for Open Systems. Backups of the database will be performed nightly using the services provided by the MGH network. All PC's run virus protection software full-time and are updated with the latest virus detection strings regularly; the Windows NT server does this as well and has the additional security of scanning all e-mail for viruses before a user can even access them. All accounts are password protected and passwords must be changed on a regular basis.

In addition, the EDC system will have an extra level of password security. At study initiation, the Data Manager will set default passwords for the relevant study personnel at the MGH NCRI and at the study site. When a new user logs in with the assigned username and default password for the first time, he or she will be forced to change the password to a unique one (at least six characters long), known only to the user. An ongoing paper log will be kept showing when usernames and passwords are set up, for whom, in what user capacity and when usernames are disabled. In case an employee forgets her/his password or a new user is added, they will submit a password request form via email to the Data Manager, who will issue a new default password. They must then go through the Change Password process. The passwords will expire every three months, when users will be required to go through the Change Password process. To avoid password-based software attacks, the system will lock a user for 1 minute if an incorrect

password is provided 3 times in a row. A user will also be able to change the password at will if he or she feels that it may have been compromised.

## **10.4 Confidentiality**

The NeuroBANK™ software and patient data reside on servers located in the Partners Healthcare Systems (Partners) server farm. Physical and software access to the servers and security is provided by the Partners IT department. Members of the NeuroBANK™ management team will do everything, within reason, to keep a participant's identity protected.

### **10.4.1 Global Unique Identifier (GUID)**

A patient Global Unique Identifier (GUID) will be used as the identifier for individuals participating in the study in NeuroBANK™. The GUID is an 11-character string that is generated using encryption technology and algorithms licensed by the NCRI from the National Institutes of Health (NIH).

The GUID is generated on a secure website that utilizes 128-bit Secure Socket Layer (SSL). Of note, this website is not linked to NeuroBANK™. The GUID is generated using an irreversible encryption algorithm – it accepts twelve identifying data elements, (e.g. last name at birth, first name at birth, gender at birth, day, month and year of birth, city and country of birth, etc.), and produces a unique random-generated character string, or GUID. No identifying information is stored in the system; it is simply used to generate the GUID. If the same information is entered again, the same GUID will be returned.

The GUID is entered into NeuroBANK™ when the patient is being created in the system. As the same patient may participate in multiple studies, NeuroBANK™ will also allow capturing a study-specific ID for the patient. For more information about NeuroBANK™ or the GUID, please go to: [www.neurobank.org](http://www.neurobank.org).

